13.4 Secondary Exploratory Endpoints

This study is not specifically powered to address the objectives of estimating favorable change in quantitative biomarker endpoints that may be related to risk for development of breast cancer.

The most critical biomarker from a breast cancer prevention standpoint is that of cell proliferation, specifically a reduction in value for participants whose baseline specimen exhibited sufficient Ki-67 staining (1% that there is the potential for a decrease). Thus, this analysis will be limited to those participants in Cohort B. Also this parameter will be analyzed first and separately from all other biomarkers. Descriptive statistics will be used to summarize the values of Ki-67 (percent of cells staining positive) in the baseline specimen, the 6-month (off-study) specimen, and the change (both absolute and relative) from baseline to off-study. For statistical analysis, the Wilcoxon signed-rank test will be used to accommodate the expected small sample size and to avoid any assumptions regarding normal distributions. Only participants who provide paired specimens evaluable for Ki-67 will be included in this analysis. However, for off-study specimens where the cell yield is so low (<100 cells per slide) that assessment of Ki-67 is not even possible, an anti-proliferative effect can be inferred. Thus, a value of 0.5% will be imputed as a reasonable compromise between imputing a value of 0% (no evidence of any proliferation) and a value of 1% (e.g., only 1 positive cell out of 100 counted). Since a non-parametric approach is used, the exact imputed value has minimal impact given that the criterion for inclusion is a baseline value of 1%. For this primary evaluation of modulation of a quantitative measure, $p < 0.05$ will be considered the criterion for statistical significance.

Should there be adequate, paired specimens, further exploration of this primary endpoint variable, relative change in Ki-67, will be accomplished by developing an appropriate model and testing covariates. If necessary, an appropriate transformation will be used in this regression.

For these possible analyses, as for the exploratory analyses below, no adjustment will be made for multiple comparisons, but the results will be interpreted with caution.

Secondary to analysis of Ki-67, other variables will be assessed that represent a wide variety of cellular, molecular, and physical factors that have been proposed to have some level of connection with the process of breast cancer development. Categorized by the “specimen” being assessed, the variables are:

Participant

- Mammographic breast density
- Weight and BMI,
- DEXA body composition and waist measurement

Blood

- Hormones
- Adipocytokines
- Bazedoxifene levels

RPFNA

- Cytomorphology (categorical)
- Peptides and phosphopeptides (proteomics)
- Gene expression (RT-qPCR)

Descriptive statistics will be used to summarize the values at baseline (prior to start of intervention), at 6 months (after completion of intervention), and the change (both absolute and relative) from baseline to off-study. Medians, ranges, and interquartile ranges will be employed for all variables, along with mean and standard deviation for variables shown to be normally distributed. As appropriate, 95% confidence intervals will also be computed.

It should be noted that these variables are anticipated to be assessed for all participants that provide paired specimens, and thus the total should be close to 40. This provides additional opportunity to achieve normal distributes and to conduct exploratory correlational analyses. Thus paired t-test will be used for normally distributed values (initial or after appropriate transform), but nonparametric tests such as the Wilcoxon signed rank test will be used when necessary

Since these analyses are considered as exploratory, no adjustments will be made for multiple comparisons and $p < 0.05$ will be considered the criterion for statistical significance. However, caution will be employed in the interpretation and presentation of the results.

Lastly, an assessment of menopause symptom relief in this cohort will be conducted using a 29 item validated Menopause Quality of Life Intervention Questionnaire and hot flash assessment. The same statistical methods as above will be employed. The intent is not statistically significant “proof” of efficacy as Duavee® is already FDA-approved for this indication.

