4.3 Inclusion Criteria for Intervention Phase

4.3.1 RPFNA Results: An RPFNA performed less than six months prior to enrollment on study that exhibits at least 500 cells on the cytology or Ki-67 slide, and a Ki-67 positivity measured on at least 500 cells that is less than 4%.

4.3.2 Baseline chemistry profile showing reasonably normal renal and hepatic function. Creatinine <2.0, Bilirubin < 2.5, and albumin > 3.4

4.3.3 Willingness to comply with study procedures.

- Willing to have a blood draw for serum to archive bioavailable estradiol, SHBG, FSH, and bazedoxifene levels as well as a chemistry profile to ensure reasonable normal organ function at baseline and 6 month visits (approximately four tubes of blood collected)
- Willing to have a DEXA scan for body composition and waist measurement at baseline and 6-8 months.
- Willing to have a repeat mammogram and RPFNA at 6-8 months following initiation of study drug
- Willing to undergo a history, physical, vitals and breast exam at baseline and 6 month visits
- Willing to be contacted by the trial coordinator at months 1 and 3 during the 6 month study period.
- Willing to complete a 29 item validated Menopause Quality of Life Intervention Questionnaire and hot flash assessment at baseline and 6 month visits
- Willing to sign and able to understand separate consents for the RPFNAs and for study participation

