5.1 Dose Regimen and Dose Groups

Open label Bazedoxifene (20 mg) plus conjugated estrogen (0.45 mg) marketed as Duavee® for six months will be given to all trial participants. There will be no randomization as this is a one arm trial. All participants will be given eight months (two months of overage) of Duavee® to allow for scheduling study procedures.

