7. CLINICAL EVALUATIONS AND PROCEDURES

7.1 Schedule of Events

SCHEDULE OF EVENTS

Evaluation/ Procedure	Pre-Study/ Screening RPFNA	Baseline	Contact End of Month 1 & 3	Month 6	Follow Up Phone Contact
Mammogram	X			X	
RPFNA for cytomorphology, Ki-67, RTqPCR, proteomics	X			X	
Fasting blood archived for SHBG, estradiol, testosterone, progesterone, FSH, adipocytokines, and Bazedoxifene levels		X		X	
Assess Eligibility	X	X			
Informed Consent		X			
Medical History		X			
Physical Exam/CBE		X			
Vital Signs/ Height and Weight, BMI, waist measurement		X		X	
29 item validated Menopause Quality of Life Intervention Questionnaire and hot flash assessment		X		X	
Blood Chemistry		X		X	
DEXA body composition and waist measurement		X		X	
Symptom Assessments		X	X	X	X
Concomitant Medications		X	X	X	X
Pregnancy test if peri- menopausal		X			
Dispense Study Agent		X			
Collect Study Agent				X	
Adverse Events			X	X	X
Telephone or Email Contact			X		X

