8.2 Secondary Endpoints

For the second Specific Aim (Does Duavee® cause a reduction in Ki-67?), we will consider only participants having baseline Ki-67 >1%; and thus the potential to experience a decrease.

Any remaining assessments of modulation due to Duavee® would be considered exploratory for purposes of informing future applications and trial designs. This would include change in breast cytomorphology index score; changes in gene expression (specifically, pS2, PGR, ER alpha, GREB-1, Amphiregulin, SDF-1, cyclin D1) by RTqPCR; changes in levels of ER alpha and cyclin D1 and possibly other proteins and phosphoproteins by proteomics; change in serum bioavailable hormones, adipocytokines, and change in menopause specific quality of life. For these analyses, all participants with paired pre-study and post-study data will be included.

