13. STATISTICAL CONSIDERATIONS

13.1 Study Design/Endpoints

The experimental design for the study is an open label, single arm pilot study of Duavee® as a prevention drug for breast cancer in high risk peri- or post-menopausal women at high risk for development of breast cancer, with Ki-67 positivity of <4%. Participants will receive Duavee® one tablet daily for six months. No randomization or stratification is involved. The primary endpoint is demonstration of feasibility for subsequent trials of Duavee® using a series of pre-set criteria having to do with accrual rate, completion, and lack of evidence for an increase in breast epithelial cell proliferation. A secondary endpoint will examine the specific potential for Duavee® to actually reduce cell proliferation and thus function as a breast cancer chemopreventive agent. A series of exploratory endpoints will document clinical efficacy (relief of vasomotor symptoms) and will examine modulation of other quantitative biomarkers potentially related to breast cancer development.

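### Section 13.4 tests for a Ki-67 fall from the same reading that selected women into Cohort B, with no control, so p<0.05 cannot by itself be attributed to Duavee

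*Combined protocol and SAP*

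**What the plan says.** Section 4.3 admits women on a screening aspirate with "a Ki-67 positivity measured on at least 500 cells that is less than 4" per cent. Section 13.2 splits them by that reading: Cohort A is below 1%, Cohort B from 1% to below 4%. In the Section 7.1 schedule the row "RPFNA for cytomorphology, Ki-67, RTqPCR, proteomics" is marked only at screening and at Month 6, so there is one aspirate before treatment. Section 5.1 states "There will be no randomization as this is a one arm trial".

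For a reduction in Ki-67, Section 13.4 says "Thus, this analysis will be limited to those participants in Cohort B". It compares baseline with off-study values by the Wilcoxon signed-rank test and sets p<0.05, introduced with the words "For this primary evaluation of modulation of a quantitative measure". Section 8.2 frames the aim as a question of cause, whether Duavee does "cause a reduction in Ki-67?), we will consider only participants having baseline Ki-67 >1%; and thus the potential to experience a decrease". Section 13.1 says the endpoint examines the drug's potential "to actually reduce cell proliferation and thus function as a breast cancer chemopreventive agent".

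If a follow-up slide has too few cells to score (under 100), Section 13.4 imputes 0.5%. It argues that, with a non-parametric test, "the exact imputed value has minimal impact given that the criterion for inclusion is a baseline value of 1" per cent.

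**The concern.** A woman enters Cohort B partly because her true Ki-67 is higher and partly because that aspirate happened to read high. The second part does not carry over to the next aspirate. If most eligible women sit below 1%, repeat readings in Cohort B will tend to be lower even if the drug does nothing. With one arm and no second pre-treatment reading, the test cannot separate that drift from a drug effect.

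Section 13.4 treats Ki-67 reduction as the most critical biomarker for prevention and analyses it first. Section 2.2 says that a finding of reduced proliferation should lead to placebo-controlled trials. A fall produced by selection could therefore be read as the signal that justifies them.

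**Working it through.** **Inputs from the documents.** 500 cells per reading (9.1.1), so 1% is 500 × 0.01 = 5 positive cells and one cell is 0.2 points. Cohort B is 1% to below 4% (13.2; Section 8.2 writes >1%). About 11% of similar clinic women show an increase untreated (13.3, which does not define increasing for this figure or give the interval). Cohort A is expected to fill faster (13.2), which suggests that most women are below 1%.

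**Not in the documents, so assumed.** The population level and spread of Ki-67, agreement between two aspirates from one woman, the number in Cohort B, and a two-sided test. If 20 of 40 women were in Cohort B, 85% completion would give 20 × 0.85 = 17 pairs; 15 is used below. Section 13.4 states no power or sample size for this test, so there is no plan figure to reproduce.

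**Direction.** To a linear approximation, with population mean μ and correlation ρ between aspirates, a woman reading x has expected untreated change −(1 − ρ)(x − μ). Take x = 1.6% and ρ = 0.5 as illustration.
- μ = 0.7%: −0.5 × (1.6 − 0.7) = −0.45 points.
- μ = 2.0%: −0.5 × (1.6 − 2.0) = +0.20 points.

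The 1% cut pulls repeat readings down and the 4% cap pulls them up. The 1% cut dominates when typical values lie below or near 1%.

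**Size, no drug effect, 15 women.** True Ki-67 is gamma-distributed between women, with extra aspirate-to-aspirate variation and binomial counts on 500 cells. Ranges cover separate runs, with and without continuity correction.

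| Mean Ki-67 / between-woman CV / aspirate CV | Untreated increase (13.3 definition) | Cohort B share of eligible | Significant falls (nominal 2.5%) |
|---|---|---|---|
| 1.0% / 0.7 / 1.0 | 11.0% | 31% | 41–43% |
| 1.4% / 0.8 / 0.6 | 11.7% | 46% | 10–13% |
| 1.9% / 0.6 / 0.3 | 9.7% | 71% | 3–4% |

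Across a wider grid (gamma and log-normal), keeping settings with 9–13% untreated increases and Cohort B under half, falls were significant in 25–51% of trials when the correlation between aspirates was below 0.3, and in 1.5–9% when it was 0.6 or more. Where Cohort B was under half, the median untreated change in Cohort B was −0.8 to 0 points, never positive. The mean can be positive, because a few high follow-up readings skew it, but the test works on ranks.

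**Is selection the cause?** A separate log-normal model, tuned to 11% untreated increases with median Ki-67 of 0.5–0.9%, gave significant falls in 9–34% of trials at n = 10 and 13–57% at n = 17. Replacing the before value by a second pre-treatment reading not used for selection brought this to 2.2–2.8% at n = 17. With an untuned median of 2.0% the excess disappeared (1–3%).

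**Cohorts A and B together.** In the settings tried, significant falls occurred in at most 1% of trials. Only the 4% cap remains, and it pulls slightly upward.

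**Imputation alone.** A Cohort B baseline is at least 1%, so the imputed difference is at most 0.5 − 1.0 = −0.5: always a fall. With before and after values exchangeable within 1–4% and 0, 1, 2 or 3 of 15 follow-ups set to 0.5%, significant falls occurred in 2.6–2.8%, 4.3–5.0%, 6.8–7.4% and 11.9–12.0% of trials. The counts imputed are assumptions.

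**The case against.** The strongest reply is that the plan never claims attribution. Section 13.4 is headed exploratory, says the study is not powered for these changes, and presents p<0.05 only as a significance criterion. Section 13.1 speaks of potential, Section 1 of a preliminary demonstration, and Section 2.2 looks to placebo-controlled trials. This limits the consequence and stands. It does not answer the point: Section 8.2 words the aim as cause, and the only threshold offered is one that selection alone can cross. The caution wording in 13.4 attaches to the covariate models and later analyses, in the context of multiple comparisons.

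A second reply is that the measurement is reliable. The alpha of 0.99 in Section 2.3 is agreement in reading stained slides. The same section calls the aspiration reproducible but gives no figure for agreement between aspirates. If that agreement is good, the excess is small; the documents do not say.

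A third is that the imputation is disclosed and its exact value matters little. That is right for the value: anything from 0 up to just under 1% gives the same sign. The remark does not cover the sign itself.

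A reader might also infer that the plan knows nothing of untreated change. That goes too far: Section 13.3 gives the 11% rate of increase. What is missing is an untreated rate of decrease.

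**Conclusion.** The point holds as a limit on attribution. The reading that selects Cohort B is the before value of an uncontrolled test, and nothing in the plan lets a significant fall be separated from regression to the mean. That conclusion needs no simulation.

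The size is open. The illustrative chance of a significant fall with no drug effect runs from about the nominal 2.5% to over 40% with 15 women. It depends on population level, repeatability and cohort size, none of which the documents give, and on reading the 11% figure by the plan's own definition of increase. A reader might take the upper figures as the test's false-positive rate, or conclude that any observed fall must be an artefact. The documents support neither. They do suggest, by expecting Cohort A to fill faster, that the pull is downward rather than upward.

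The imputation is a separate, smaller problem in the same direction. The change is worth making, but the stakes are modest: the endpoint is exploratory, unpowered and not a feasibility criterion, and a later placebo-controlled trial would expose an error.

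**What to change.** In Section 13.4:

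1. Keep the signed-rank p-value as a descriptive result and add a sentence such as: *Because Cohort B is selected on the baseline reading and there is no control, a fall, including one with p<0.05 or an interval excluding zero, may reflect regression to the mean and will not by itself be attributed to Duavee.*
2. Report the median absolute and relative change in Cohort B with a 95% interval, with and without imputed values, and give the number imputed.
3. Show alongside the paired change across Cohorts A and B together, from scored slides only. This removes selection at the 1% cut. The 4% cap remains and pulls slightly upward, and many Cohort A women have little room to fall, so the absence of a fall here would not rule out a drug effect.
4. Optionally, if the clinic records behind the 11% figure are adequate, show the untreated change in women with a baseline of 1% to below 4%, with their number and repeat interval.

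The cost is wording and two extra table rows, plus one small table for item 4. No new samples, visits or slide reading are needed, since both cohorts already supply paired Ki-67 for Section 13.3. The downside is that the reduction result becomes a weaker, descriptive statement.

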13.5 Reporting and Exclusions

All participants who receive any Duavee® will be analyzed for adverse events. For biomarker modulation, all participants that have evaluable pre-study and post-study specimens and assessments will be included in the analysis,

Compliance will be determined by tablet counts, which will be done at the end of treatment. Participants that maintain 70% compliance throughout the duration of the trial will be considered “compliant”. Compliance, in terms of the number of tablets missed and percent of participants compliant, will be summarized with descriptive statistics. Supporting tests for the analyses will

be performed including only these participants who are compliant and have taken Duavee® for at least 3 months and have taken Duavee® within 2 weeks prior to the post-study aspiration.

13.6 Interim Analysis

There will be no formal interim analysis of the endpoints of the study. Particularly, the quantitative endpoints (other than cytomorphology and Ki-67) are routinely batch-processed at the completion of study with pre- and post-intervention samples assayed together. However, it is possible that the feasibility endpoints could be evaluated early. For example, if six participants drop out of the study early, one would not require enrolment of the full planned 40 participants to conclude that the drop-out rate of 15% was unacceptably high. If it becomes obvious that the trial will not demonstrate feasibility, then accrual to the trial can be terminated early.

Safety data will be reviewed quarterly by the KUMC KUCC Data Safety and Monitoring Committee.

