1.1 Primary Feasibility Objective

To determine feasibility for a larger clinical trial in women at moderately increased risk we will:

1.1.1 Determine if accrual is brisk as demonstrated by accrual of at least 20 moderate risk women in the initial 6 months (3.5 entrants per month) in a single institution;

1.1.2 Determine if there is a 15% or lower dropout rate over the 6 month intervention; and

1.1.3 Determine if 20% or fewer women with paired RPFNA specimens exhibit a meaningful increase in benign breast cell proliferation (Ki-67) where meaningful increase is defined as an increase in Ki-67 to 2% or higher in individuals with initial Ki-67 < 1% or a doubling of Ki-67 in individuals with initial Ki-67 of 1% or higher.

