8. CRITERIA FOR EVALUATION AND ENDPOINT DEFINITION

8.1 Primary Endpoint

Prior to formal analysis, there are two aspects of a feasibility trial that are based on simple numbers. If we cannot accrue 40 eligible women within a reasonable time (no more than 12 months) and/or if more than 15% of enrolled participants do not complete the study, then it would not be practical to propose future studies.

For the Specific Aim of documenting that Duavee® does not cause a meaningful increase in proliferation, only participants for whom paired specimens evaluable for Ki-67 will be included. An increase in Ki-67 will be defined by one of two scenarios: a) from a baseline Ki-67 <1% to a Ki-67 >2%; or b) for a baseline Ki-67 >1%, at least a doubling of the baseline value.

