13.2 Primary Feasibility Endpoints

The primary endpoint overall is an assessment of feasibility that will inform the decision about and the design of subsequent trials. This will be based on considerations of 1) ease of accrual of the target population; 2) acceptance and tolerability of the intervention. Basically, if either fail, then it would indicate that future trials with this approach are not feasible to consider

For the first aspect of accrual, a criterion has been set at 20 participants accrued in 6 months (starting from when the trial is actually open to enrollment). If the accrual rate is slower than this, it would be impractical to conduct a similar trial at a single institution. While total accrual will be used for this initial criterion, the relative ease of accrual into the two cohorts (Cohort A, Ki-67<1%; Cohort B, 1% ≤ Ki-67 < 4%) will be taken into consideration. Certainly it is anticipated that accrual to Cohort A will be easier and faster, but if accrual to Cohort B is not at least half the overall rate (i.e., 20 participants per 12 months) then it would indicate that a trial requiring measurable Ki-67 >1% would not be a feasible option. For this assessment, accrual is considered as meeting all eligibility criteria, signing an informed consent, and receiving the first dose of study agent. This number will then be used for consideration of the second feasibility aspect.

The second aspect of feasibility is retention of participants on trial, completion of the planned 6 months of intervention, and acquisition of repeat RPFNA specimen (plus blood, mammogram, etc.) for assessment of modulation in quantitative biomarkers. A criterion has been set at 85% completion overall. While the ultimate goal is paired samples for comparison of biomarkers (for sample size and power calculation purposes), a high incidence of early problems with participant compliance in general (adverse events, complaints about the study agent or the schedule, etc.) would serve as an indication that the intervention would not be suitable for future trials.

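### Section 13.6 treats six drop-outs as failing the retention criterion, but six of 40 is exactly 15%, which passes; the first certain failure is seven

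*Combined protocol and SAP*

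**What the plan says.** Retention is part of the primary feasibility endpoint, and four sections fix its boundary for the planned 40 participants:

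- Section 1.1.2: "Determine if there is a 15% or lower dropout rate over the 6 month intervention". Exactly 15% passes.
- Section 8.1: "if more than 15% of enrolled participants do not complete the study, then it would not be practical to propose future studies". Failure needs more than 15%.
- Section 13.2: "A criterion has been set at 85% completion overall". The denominator is every participant accrued, meaning eligible, consented and given a first dose.
- Section 13.3 takes 34 paired specimens as the minimum that follows from the retention criterion, which is 40 minus 6.

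Section 13.6 plans no formal interim analysis but allows the feasibility endpoints to be looked at early. Its example is that "if six participants drop out of the study early, one would not require enrolment of the full planned 40 participants to conclude" the matter; in its own terms, to "conclude that the drop-out rate of 15% was unacceptably high". It continues: "If it becomes obvious that the trial will not demonstrate feasibility, then accrual to the trial can be terminated early".

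On accrual, section 13.2 states that "a criterion has been set at 20 participants accrued in 6 months". Section 1.1.1 gives the same count and adds a rate of 3.5 entrants per month.

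**The concern.** The example in section 13.6 sits on the wrong side of the boundary that the other sections set. Its argument is that the result can be known before all 40 women are enrolled. That is true only once the count can no longer end as a pass. At six drop-outs it still can, if nobody else is lost.

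Section 13.2 judges feasibility by pre-set success and failure values and not by a formal test. The boundary is therefore the decision rule and should read the same throughout. If the example were followed literally, accrual could be ended at a count that sections 1.1.2 and 8.1 accept. A final count of exactly six would also be a pass under those sections and unacceptable under 13.6.

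**Working it through.** **Inputs.** Planned enrolment 40 (schema, section 3). Limit of 15% drop-out, inclusive (1.1.2, 8.1). 85% completion (13.2). Minimum of 34 pairs (13.3). Six drop-outs (13.6).

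**The plan's own figures.** Drop-out rate = d/40, so 6/40 = 15.0%, the rate that 13.6 names. Minimum completers = 0.85 × 40 = 34, the number in 13.3. Both reproduce.

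**Position of the boundary.**

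| Drop-outs | Drop-out rate | Completers | Against 1.1.2 and 8.1 |
|---|---|---|---|
| 5 | 12.5% | 35 (87.5%) | pass |
| 6 | 15.0% | 34 (85.0%) | pass |
| 7 | 17.5% | 33 (82.5%) | fail |

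**Probability of ending on the disputed count.** This is P(X = 6) = P(X ≥ 6) − P(X ≥ 7) for a binomial with n = 40. The true drop-out rates are assumed.

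- 10%: 20.63% − 9.95% = 10.7%.
- 15%: 56.75% − 39.33% = 17.4%.

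This is how often the sections would disagree about the final result. It is not the probability of a wrong early closure, which needs timing as well.

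**Probability of a wrong closure.** This was found by simulation, 400,000 trials per setting. Assumptions, none of them given in the documents: 40 women enter evenly or at uniform random times over 6 months (the plan in section 3) or 12 months (the limit in 8.1); each drops out with probability p; drop-out time is uniform over 6 months on agent. A closure is wrong if the sixth drop-out comes before the 40th enrolment and the full 40 would have had exactly six drop-outs.

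| Accrual | p = 0.10 | p = 0.125 | p = 0.15 |
|---|---|---|---|
| 6 months, even / random entry | 0.12% / 0.13% | 0.18% / 0.18% | 0.22% / 0.20% |
| 12 months, even / random entry | 1.59% / 1.53% | 2.30% / 2.24% | 2.58% / 2.55% |

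Repeat runs with slightly different spacing of the entries moved the upper ends to 0.23% and 2.7%. Among trials that reach six drop-outs before accrual ends, closing is wrong in about 3% to 12% (6 months) or 9% to 23% (12 months). In wrongly closed trials, about 3 to 5 women on average were still to be enrolled.

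**Accrual rate in 1.1.1.** 20/6 = 3.33 per month, and 3.5 × 6 = 21. The figure of 40 within 12 months in 8.1 also gives 40/12 = 3.33. The 6.7 per month in section 4.6 is an expectation (40/6), not a criterion.

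**The case against.** The best defence is that 13.6 gives an illustration and not a rule. It disclaims a formal interim analysis, attaches no binding count, and asks only that failure be obvious. Six losses before full enrolment already exceed 15% of those accrued (6/30 = 20.0%, 6/39 = 15.4%), and more may follow. On the figures above, 77% to 97% of closures at six would have ended in failure anyway. Section 13.2 also treats a high incidence of early compliance problems as a warning in its own right.

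The assumed drop-out of 10% to 15% is at or above what the plan expects: section 4.6 expects less than 10%, and section 3 expects 36 of 40 to complete. At 5% the chance of wrong closure falls to about 0.01% (6 months) and 0.16% (12 months), although roughly a third and a half of those rare closures would be wrong.

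All of this bears on importance, and it stands. It does not rescue the sentence. Section 13.6 does not argue from a running rate. It calls 15% itself too high, and that rate is six over the planned 40. Section 13.2 uses all accrued participants as the denominator, so the final rate after six early losses can still be exactly 15%. It is also fair to say that the 3.5 per month is a parenthetical gloss on an explicit count, and no decision depends on it.

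**Conclusion.** The inconsistency is real and minor. Section 13.6 is stricter by one drop-out (six against seven of 40) than the criterion stated in 1.1.2 and 8.1 and carried into 13.3. This rests on arithmetic alone. The estimate of consequence rests on assumed drop-out rates, entry pattern and drop-out timing: about 0.1% to 0.2% of trials wrongly closed with the planned 6-month accrual, and 1.5% to 2.7% if accrual takes 12 months. The endpoint definition, analysis and sample size are unaffected. The 3.5 per month in 1.1.1 is a separate, near-clerical slip.

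**What to change.** In section 13.6, change six to seven, and replace the statement that a 15% rate was too high with one that the drop-out rate would exceed the 15% limit. In section 1.1.1, change 3.5 to 3.3 entrants per month and keep 20 in 6 months.

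This follows the boundary that the other sections share. If the investigators instead meant exactly 15% to fail, 1.1.2, 8.1, 13.2 and 13.3 must change to require less than 15%, which means at least 35 completers (35/40 = 87.5%). Either way the sections should agree.

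The recommended change is three small wording edits. It needs no new data, no change in sample size and nothing further from participants.
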